7.2.1. Multiple Myeloma

7.2.1.1. Endpoint / Variables

7.2.1.1.1. Overall Response Rate

Overall Response Rate (ORR), is defined as the percentage of responders (subjects with confirmed stringent complete response (sCR), complete response (CR), very good partial response (VGPR), and partial response (PR) as assessed according to 2011 International Myeloma Working Group (IMWG) criteria (Appendix 1 in the protocol)). Only the assessments from the start of treatment up to the earlier of disease progression or the start of new anti-cancer therapy will be considered. Only new systemic anti-cancer drugs taken are considered as anti-cancer therapy (radiotherapy and surgeries are not considered as systemic anti-cancer therapy for the purpose of this analysis). .

Subjects with only one assessment (therefore not confirmed), or assessments of Not Evaluable or missing response will be treated as non-responders; i.e. they will be included in the denominator when calculating the percentage.

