7.3.1.2. Summary Measure

7.3.1.2.1. Progression-Free Survival

PFS is defined as the interval of time between the date of first dose and the earlier of the date of first disease progression and the date of death due to any cause. Disease progression will be based on the assessments by the Investigator.

If there is no adequate baseline assessment, the subjects will be censored at their date of first dose. Subjects without any adequate post-baseline tumor assessments will be censored at the date of first dose.

Subjects who progressed or died after an extended period without adequate assessment will be censored at their date of last adequate assessment prior to progression or death even if subsequent information is available regarding progression or death. An adequate assessment is defined as an assessment where the Investigator determined response is sCR, CR, VGPR, PR, MR or SD. The date of response at that assessment will be used for censoring. As the assessment schedule may change through the course of the protocol, specific rules for identifying extended loss to follow-up or extended time without an adequate assessment are provided in Section 16.5.4.

For subjects who receive subsequent anti-cancer therapy the following rules will apply:

- If the start date of the anti-cancer therapy is partial (i.e. either missing the day but has the month and year available or missing both day and month), the imputation rules described in Section 16.7.2.1 will be applied. No imputation will be made for completely missing dates.
- If anti-cancer therapy is started without documented disease progression or death OR is started prior to documented disease progression or death, then PFS will be censored at the date of the last adequate assessment that is no later than the date of initiation of anti-cancer therapy (i.e. if an assessment occurs on the same day as the start of new anti-cancer therapy the assessment will be used - as it will be assumed the assessment occurred prior to the administration of new anti-cancer therapy). The date of response at the last adequate assessment will be used as the censoring value.
- If a subject has only a baseline visit or does not have an adequate assessment that is no later than the date of initiation of anti-cancer therapy, PFS will be censored at the date of first dose.

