7.3.1.2.4. Time to Response

Time to Response (TTR) is defined as the time from first dose to the first documented evidence of confirmed PR or better, among subjects who achieve a response (i.e., confirmed PR or better).

TTR will be summarized using Kaplan-Meier method. If data permits, median TTR, first and third quartiles and 95% CI, will be estimated using the Brookmeyer-Crowley method [Brookmeyer, 1982]. A listing of TTR time will also be provided. Summary of TTR will be based on Part 2 MM population; listing of TTR will be based on All Treated MM population.

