TOTAUC	Total AUC (ug.day/mL)		(Total dose received)/Individual Clearance of ADC	popPK output
Q4TOTAUC	Quartile of TOTAUC	0,1,2,3		derived
Q5TOTAUC	Quintile of TOTAUC	0,1,2,3,4		derived
MMAFAUC	First dose AUC(0-inf) of MMAF (ug.day/mL)		First dose (mg)/Individual Clearance of MMAF	popPK output
Q4MMAFAUC	Quartile of MMAFAUC	0,1,2,3		derived
Q5MMAFAUC	Quintile of MMAFAUC	0,1,2,3,4		derived
MMAFTOTAUC	Total AUC (ug.day/mL)		(Total dose received)/Individual Clearance of MMAF	popPK output
Q4MMAFTOTAUC	Quartile of MMAFTOTAUC	0,1,2,3		derived
Q5MMAFTOTAUC	Quintile of MMAFTOTAUC	0,1,2,3,4		derived

For efficacy

Column Header	Data Item	Codes	Derivation/Comments	Source data set
C	Exclusion identifier	Row Number DORDM	Set to line/row number unless one or more of the following conditions are met, then set to code: 
 DORDM: If DORD is missing 	adtte
STUDY	Study ID		1 = BMA117159	adsl
SUBJID	Subject identifier from source data		SUBJID = SUBJID	adsl
ID	NONMEM subject identifier		Sequential subject identifier across studies after data is sorted by SUBJID. Starting with P	derived
PFSCFLCD	PFS Censoring Flag Code	0 or 1	For PARAMCD=PFS_D, CNSR value is assigned to PFSCFLCD 0=Event 1=Censor	adtte
PFSD	PFS (Days)		For PARAMCD=PFS_D, AVAL value is assigned to PFSD	adtte
PFSM	PFS (Months)		For PARAMCD=PFS_M, AVAL value is assigned to PFSM	adtte
PFSY	PFS (Years)		For PARAMCD=PFS_D, (AVAL/365) value is assigned to PFSY	derived
TTRCFLCD	TTR Censoring Flag Code	0 or 1	For PARAMCD=TTR_D, Assign 1 to TTRCFLCD. For subjects where TTR_D is missing, assign 0 to TTRCFLCD.	adtte
TTRD	TTR (Days)		For PARAMCD=TTR_D, AVAL value is assigned to TTRD. For subjects where TTR_D is missing, assign PFSD to TTRD.	adtte
TTRM	TTR (Months)		For PARAMCD=TTR_M, AVAL value is assigned to TTRM. For subjects where TTR_M is missing, assign PFSM to TTRM.	adtte
TTRY	TTR (Years)		For PARAMCD=TTR_D, (AVAL/365) value is assigned to TTRY. For subjects where TTR_D is missing, assign PFSY to TTRY.	derived
DORCFLCD	DOR Censoring Flag Code	0 or 1	For PARAMCD=DOR_D, CNSR value is assigned to DORCFLCD 0=Event 1=Censor Assign "." for missing.	adtte
DORD	DOR (Days)		For PARAMCD=DOR_D, AVAL value is assigned to DORD. For subjects where DOR_D is missing, assign "."	adtte

Column Header	Data Item	Codes	Derivation/Comments	Source data set
DORM	DOR (Months)		For PARAMCD=DOR_M, AVAL value is assigned to DORM. For subjects where DOR_M is missing, assign “.”	adtte

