16.10.2.2.2. Clinical Response

Presence or absence of clinical response will be described using a conventional logistic regression model. Time to response will be explored using Kaplan Meier plots with exposure subdivided into quartiles and quintiles.

PFS will be explored using Kaplan Meier plots with exposure subdivided into quartiles and quintiles and occurrence of progression may also be described using a conventional logistic regression model.

Duration of response will be explored using Kaplan Meier plots with exposure subdivided into quartiles and quintiles.

Best clinical response will be analyzed using an ordered logistic regression, with response categorized from 0 (progressive disease) to 6 (stringent complete response). Exposure will be treated as a categorical variable subdivided into quartiles and quintiles.

In the ordered logistic regression analyses, the use of categorical measures of exposure in lieu of continuous variables will allow for non-parametric descriptions of response functions.

Best clinical response as assessed by maximum reduction in M-protein or FLC will be analyzed by exposure (continuous and/or by quartile and quintile of exposure).

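### The exposure-response time-to-response plots censor non-responders at progression or death, so the Kaplan-Meier curves overstate response if read as response probabilities

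*SAP*

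**What the plan says.** The efficacy table in SAP 16.10.1 sets the time-to-response variables. Responders are flagged by "For PARAMCD=TTR_D, Assign 1 to TTRCFLCD". For everyone else, "For subjects where TTR_D is missing, assign 0 to TTRCFLCD" and "For subjects where TTR_D is missing, assign PFSD to TTRD"; the month and year versions follow the same pattern. The flag has no code key. The neighbouring PFS flag has one ("CNSR value is assigned to PFSCFLCD 0=Event 1=Censor"), and the DOR flag uses the same coding.

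SAP 7.3.1.2.1 ends PFS at the "earlier of the date of first disease progression and the date of death due to any cause". For a subject who starts new anti-cancer therapy first, PFS is censored at the last adequate assessment on or before the therapy start.

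SAP 7.2.1.1.1 limits the assessments that can count as a response to those "up to the earlier of disease progression or the start of new anti-cancer therapy will be considered".

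SAP 16.10.2.2.2 then states: "Time to response will be explored using Kaplan Meier plots with exposure subdivided into quartiles and quintiles". It names no competing-risk method. The main time-to-response summary in SAP 7.3.1.2.4 is restricted to confirmed responders.

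**The concern.** A non-responder whose PFS time is a progression or death has left the set of subjects who can have a counted response. The same is true after new anti-cancer therapy. These are competing events. Coding them as censoring tells Kaplan-Meier that the subject might still respond later, at the rate of those still at risk. One minus Kaplan-Meier (1-KM) then describes response in a setting without progression, death or new therapy, and not the proportion of treated subjects who respond.

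The plots exist to compare exposure groups. If exposure acts partly by delaying progression, and so leaves more time to respond, curves that censor progression remove that part of the difference from view.

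**Working it through.** The SAP gives no figure for this analysis, so there is none to reproduce. The check compares 1-KM, with progression or death censored, against the cumulative incidence of response, with progression or death as a competing event.

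**Inputs.** Response rates of 20% and 40% are the design values in SAP 2.4 and 3.1.2.1.1; 40 is the maximum MM expansion cohort there. The hazards, the time to first event and the visit counts below are assumptions, because the SAP gives none.

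**Formulas.** With constant monthly hazards r (response) and p (progression or death):
- cumulative incidence at t = r/(r+p) × [1 − exp(−(r+p)t)]
- 1-KM at t = 1 − exp(−rt)

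**Single cases.**
- r = 0.2, p = 0.3 (eventual response 40%), 6 months: 0.4 × (1 − exp(−3)) = 0.380, against 1 − exp(−1.2) = 0.699. Gap 32 points.
- r = 0.1, p = 0.4 (eventual response 20%), 6 months: 0.2 × (1 − exp(−3)) = 0.190, against 1 − exp(−0.6) = 0.451. Gap 26 points.
- r = 0.15, p = 0.225 (eventual response 40%), 3 months: 0.4 × (1 − exp(−1.125)) = 0.270, against 1 − exp(−0.45) = 0.362. Gap 9 points.

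**Range at 6 months, 40% response**, by median time to the first of response or progression/death:
- 1 month: 0.394 against 0.811
- 2 months: 0.350 against 0.565
- 3 months: 0.300 against 0.426

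The excess is therefore 13 to 42 points. A simulation of 200,000 subjects for the 2-month case gave 0.350 against 0.565.

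**Forty subjects, no constant-hazard assumption.** Responses at five visits are 8, 4, 2, 1, 1 (16 in all) and progressions 6, 6, 4, 4, 4 (24 in all), so the numbers at risk are 40, 26, 16, 10 and 5. Then 1-KM = 1 − (32/40)(22/26)(14/16)(9/10)(4/5) = 0.574, against 16/40 = 0.400. If all 24 progressions come after the last response, both equal 0.400.

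**Early responses.** With 40% response, responses at the first three 3-weekly visits, median progression of non-responders 2 to 6 months after the first visit, and 18 subjects per stratum, simulated mean 1-KM at 6 months is 41% to 46%: an excess of 1 to 6 points.

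**Comparing strata.** Take r = 0.2 in three strata with p = 0.05, 0.2 and 0.4. At 6 months cumulative response is 0.621, 0.455 and 0.324, while 1-KM is 0.699 in all three.

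**The case against.** The strongest defence is that censoring competing events is legitimate for the cause-specific response hazard, which is itself a reasonable exposure contrast. The SAP never says that the curves will be read as response proportions. SAP 16.10.2.2.2 covers those through logistic regression of response and ordered logistic regression of best response, neither of which uses this time variable. The plot is exploratory, has no planned test, and belongs to work reported separately (SAP 12.1). All of this stands and limits the weight of the point. It does not make the plotted curve a response probability, which is how a Kaplan-Meier plot of time to response is usually read.

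Some stronger readings are tempting and are not supported:
- A reader might infer that early progression in low-exposure groups raises their curves. It does not: the formula for 1-KM contains no progression hazard. Faster progression only widens the gap to actual response.
- A reader might assume that most non-responders have progression or death as their PFS time. The SAP gives no split. PFS is also censored for ongoing follow-up, missing adequate assessments, new therapy and gaps of more than 49 days (SAP 7.3.1.2.1 and 16.5.4).
- A reader might see a conflict with the responders-only definition in SAP 7.3.1.2.4. That is a different summary for a different purpose and not a defect.

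**Conclusion.** The point holds for the exposure-response time-to-response plots. Under the derivation as written, 1-KM exceeds actual cumulative response whenever a progression or death precedes a later response in the same stratum. Subjects who start new therapy without a response add to this. The direction follows from the SAP's own rules. The size does not: it runs from near zero when responses come first to over 30 points at 6 months under constant hazards with 40% response, so no single figure should be quoted as the bias.

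This takes flag value 1 as response and 0 as non-event, the only reading that makes the variable a time to response. Because the flag runs opposite to the PFS and DOR flags and has no key, a programmer who applied their key would censor responders and count non-responders as events: in the 40-subject example, 40 − 16 = 24 false events.

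It should not be inferred that the plan's response conclusions are compromised. ORR, its exact confidence interval, the logistic regressions and the responders-only summary do not depend on this rule.

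**What to change.** In SAP 16.10.1, replace the two-level flag with a keyed three-level status:
- 1 = confirmed response
- 2 = progression, death or new anti-cancer therapy without a response, at the date of that event
- 0 = censored at the last adequate assessment without a response

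Derive TTRD, TTRM and TTRY to match. For new therapy the time must come from the therapy start date, because PFSD holds the last adequate assessment for those subjects. SAP 16.7.2.1 already gives rules for partial therapy dates. State the key beside the variable, since it will differ from PFSCFLCD and DORCFLCD.

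In SAP 16.10.2.2.2, replace the Kaplan-Meier time-to-response plots with cumulative incidence (Aalen-Johansen) plots by the planned exposure quartiles and quintiles.

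The cost is SAP wording, one status variable, re-derivation of three time variables and a different plotting routine. No new data are needed.

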16.10.2. Pharmacokinetic / Pharmacodynamic Methodology

The primary goal of this analysis is to characterize the pharmacokinetic/pharmacodynamic relationships for GSK2857916 administered IV in subjects with multiple myeloma. In these analyses, drug plasma concentration (or pharmacokinetic parameter) data and pharmacodynamic data will be subjected to nonlinear mixed effects modelling using suitable software. The influence of subject demographics and baseline characteristics, including disease activity, in this population may be investigated. This analysis will be performed by CPMS and reported separately.

16.10.2.1. PD Model of sBCMA Binding

Soluble and complex BCMA levels will be log-transformed and described using a conventional linear mixed effects model and planned time for Cycle 1. Ratio to pre-dose Cycle 1 will be estimated. If data permit, parameter values will be estimated. In addition, prediction of free sBCMA data using a quasi-steady-state approximation (QSSA) PK/PD reaction binding model may be conducted without parameter estimation.

16.10.2.2. Exposure-Response Analyses**16.10.2.2.1. Corneal Toxicity**

Presence or absence of corneal toxicity will be described using a conventional logistic regression model for both \geq Grade 1 and \geq Grade 2 toxicity. Time to first corneal toxicity will be explored using Kaplan Meier plots with exposure subdivided into quartiles and quintiles. Severity of corneal toxicity will be analyzed using an ordered logistic regression model assuming Grades 0 (no toxicity), 1, 2 and 3, with exposure subdivided into quartiles and quintiles.

16.10.2.2.2. Clinical Response

Presence or absence of clinical response will be described using a conventional logistic regression model. Time to response will be explored using Kaplan Meier plots with exposure subdivided into quartiles and quintiles.

PFS will be explored using Kaplan Meier plots with exposure subdivided into quartiles and quintiles and occurrence of progression may also be described using a conventional logistic regression model.

Duration of response will be explored using Kaplan Meier plots with exposure subdivided into quartiles and quintiles.

Best clinical response will be analyzed using an ordered logistic regression, with response categorized from 0 (progressive disease) to 6 (stringent complete response). Exposure will be treated as a categorical variable subdivided into quartiles and quintiles.

In the ordered logistic regression analyses, the use of categorical measures of exposure in lieu of continuous variables will allow for non-parametric descriptions of response functions.

Best clinical response as assessed by maximum reduction in M-protein or FLC will be analyzed by exposure (continuous and/or by quartile and quintile of exposure).

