 - Categorical covariates such as gender, race, disease status, immunogenicity status, and geographic region.
- Non-parametric bootstrapping may be performed to test model robustness. The model performance may be evaluated by performing predictive check.
- Individual *post hoc* estimated PK parameters will be summarized descriptively.
- Individual subject PK parameters and exposure measures for Cycle 1 will be estimated and documented for the purposes of any subsequent exposure-response (PK/PD) analyses.

Any analyses not described *a priori* but undertaken based on emerging data will be described in detail in the report.

Data handling considerations are summarized below:

- Drug concentration data which are below the lower limit of quantification, LLQ, (NQ or BLQ) are not reported as a numeric value. Such NQ observations will be either discarded or handled in a special way. When the frequency of NQ is small, the NQ values will be excluded, since discarding NQ values in this case introduces little bias [Beal, 2001]. In situations where there are a large percentage of NQ values, other strategies which may reduce estimation bias will be considered [Beal, 2001; Hing, 2001; Ahn, 2008]. The total number and percentage of NQ values will be calculated and the rationale for the method for handling these NQ values will be documented in the final report. In situations with large number of NQ values, the predictive performance of the model will be assessed to compare the agreement between observed versus predicted proportion of samples below the LLQ.
- Concentrations that are inconsistent pharmacokinetically with the drug concentration-time profile within an individual may be considered as outliers and subsequently excluded from the dataset or analysis. Visual inspection of individual and pooled data and weighted residuals during analysis may be used to identify such outliers. Any such exclusion will be reported and discussed in the analyses summary.
- Missing data will be handled in the following way:
- Subjects who withdrew from the study and did not provide any PK samples and do not have adequate sampling and/or covariate information will be excluded from the analysis.
- If dosing and/or sampling times are missing, the relevant concentrations may be excluded from the analysis dataset and summarized in an exclusion listing file. Alternatively, the nominal times of the respective doses and/or samples may be utilized.

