DORY	DOR (Years)		For PARAMCD=DOR_D, (AVAL/365) value is assigned to DORY. For subjects where DOR_Y is missing, assign “.”	derived
ORDRESP		0,1,2,3,4,5,6	For PARAMCD=BCRSP, assign 0 for PD 1 for SD 2 for MR 3 for PR 4 for VGPR 5 for CR 6 for sCR	adrs
MAXPRED			Obtain AVAL for PARAMCD=MAXPRED. When AVAL is missing, MAXPRED = -999	adrs
RESPRATIO	Transform MAXRED to a ratio to baseline		
RESPRATIO = $\max((100+\text{MAXPRED})/100, 0.001)$
 
 When MAXRED is missing, MAXRED = -999 and RESPRATIO = -99 When MAXRED is less than -100 e.g. -100.15, RESPRATIO = negative (It is negative but greater than -8.99), then update RESPRATIO = 0.001 When MAXRED is equal to -100, RESPRATIO = 0, then update RESPRATIO = 0.001 	adrs, derived
RSPTYP	Response Type	1,2,3	1 for Serum M-Protein 2 for Serum FLC 3 for Urine M-Protein	adrs
CUMAMTP	Cumulative dose to PFS (mg)		For progression that occurred on dosing days, the dose on the progression day was not included in the cumulative dose calculation.	adex, adtte
Q4CUMAMTP	Quartile of CUMAMTP	0,1,2,3		derived
Q5CUMAMT	Quintile of CUMAMTP	0,1,2,3,4		derived
CUMAUCP	Cumulative AUC to progression (ug.day/mL)		(Cumulative dose to progression)/Individual Clearance of ADC	popPK output, adtte
Q4CUMAUCP	Quartile of CUMAUCP	0,1,2,3		derived
Q5CUMAUCP	Quintile of	0,1,2,3,4		derived

Column Header	Data Item	Codes	Derivation/Comments	Source data set
	CUMAUCP			
TAAUCP	Time-average AUC till progression (AUC/day)		The area under the plasma ADC concentration–time curve (AUC) per day (AUC/day) will be derived for each patient using the available ADC dosing information, individual patient oral clearance (CL/F) values from the population pharmacokinetic model, and the time to the occurrence of the PFS	popPK output, adtte
Q4TAAUCP	Quartile of TAAUCP	0,1,2,3		derived
Q5TAAUCP	Quintile of TAAUCP	0,1,2,3,4		derived
CUMAMTR	Cumulative dose to Response (mg)		For response that occurred on dosing days, the dose on the response day was not included in the cumulative dose calculation.	adex, adtte
Q4CUMTAMTR	Quartile of CUMAMTR	0,1,2,3		derived
Q5CUMTAMTR	Quintile of CUMAMTR	0,1,2,3,4		derived
CUMAUCR	Cumulative AUC to response (ug.day/mL)		(Cumulative dose to response)/Individual Clearance of ADC	adex, adtte, popPK output
Q4CUMAUCR	Quartile of CUMAUCR	0,1,2,3		derived
Q5CUMAUCR	Quintile of CUMAUCR	0,1,2,3,4		derived

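### Exposure-response plots do not name the exposure metric, and the dataset supplies quartiles of exposure accumulated up to the event, which produce false trends

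*SAP*

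**What the plan says.** Section 16.10.2.2.2 says "PFS will be explored using Kaplan Meier plots with exposure subdivided into quartiles and quintiles" and "Duration of response will be explored using Kaplan Meier plots with exposure subdivided into quartiles and quintiles". Time to response gets the same treatment, and section 16.10.2.2.1 does likewise for time to first corneal toxicity. Logistic and ordered logistic models accompany the plots. Neither section names an exposure variable.

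Section 16.10.1 supplies two kinds of candidate, each with quartile and quintile codes:

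- **Outcome-dependent:** cumulative dose, cumulative AUC and time-average AUC up to PFS, response, end of response and corneal event, plus total dose and total AUC. For PFS the entry "Quartile of CUMAMTP" sits beside the counting rule: "For progression that occurred on dosing days, the dose on the progression day was not included in the cumulative dose calculation".
- **First-cycle:** first-cycle amount, initial dose, Cycle 1 end-of-infusion Cmax, first-dose AUC, and Ctau observed before the Cycle 2 dose.

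Section 16.9.2 points to the second kind: individual parameters and "exposure measures for Cycle 1 will be estimated and documented for the purposes of any subsequent exposure-response (PK/PD) analyses". Section 16.7.2 notes that length of treatment depends on endpoints such as progression. No section gives a landmark, a time-varying method or a warning about circularity.

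**The concern.** A subject who progresses late receives more doses before progressing. If subjects are grouped by dose or AUC accumulated up to progression, the grouping variable is partly caused by the outcome on the time axis. A Kaplan-Meier plot by such quartiles then shows strong separation whether or not exposure matters.

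The direction depends on the metric and the outcome:

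- For PFS and DOR, cumulative or total exposure looks beneficial.
- For time to response, cumulative exposure to the event makes higher exposure look slower.
- For corneal toxicity, cumulative exposure to the event makes higher exposure look protective.
- For PFS, time-average AUC to progression makes higher exposure look harmful.

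Relating exposure to safety and clinical activity is a listed exploratory objective (section 2.2), and these plots are its main display. With the metric open, an artefact of either sign can be read as an exposure-response relation.

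**Working it through.** The SAP gives no figure for these plots, so there is none to reproduce. The check asks what each grouping shows when exposure has no effect.

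**Inputs from the SAP.** Part 2 MM dose 3.40 mg/kg (5.1); dosing every 21 days (6.5); visits scheduled to Cycle 16 (16.2.3.1), taken as at most 16 doses; maximum MM expansion size 40 (3.1.2.1.1); event-day dose not counted (16.10.1).

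**Assumptions, not in the SAP.** Exponential PFS, unrelated to exposure; log-normal clearance, log-SD 0.3; log-normal weight, log-SD 0.2; dosing stops at progression.

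**Formulas.** For an event on day t after first dose:

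- doses before the event: n(t) = min(ceil(t/21), 16)
- first-dose AUC: A = dose/CL
- cumulative AUC to event: n(t) × A
- time-average AUC: n(t) × A / t

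**By hand.** Take subjects with identical A.

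- Progression on day 42: ceil(42/21) = 2 doses, so cumulative AUC is 2A.
- Progression on day 252: ceil(252/21) = 12 doses, so 12A. Identical first-dose exposure, six times the cumulative exposure, solely from later progression.
- Time-average AUC runs the other way. On day 10 it is A/10 = 0.100A per day; on day 252 it is 12A/252 = 0.048A; on day 630, after the 16-dose limit, 16A/630 = 0.025A.

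**Large-sample null simulation, no dose changes or censoring; median PFS in months:**

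| True median | Cumulative AUC to PFS, Q1 | Cumulative AUC to PFS, Q4 | First-dose AUC, every quartile |
|---|---|---|---|
| 3 | 0.6 | 8.6 | about 3 |
| 8 | 1.6 | 16.0 | about 8 |
| 12 | 2.3 | 20.3 | about 12 |

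Pooling an assumed mix of Part 1 and Part 2 doses leaves 1.8 versus 15.5 months at a true median of 8.

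**Trial-size null simulation.** N = 40, with 75 as a second, assumed size; true median 3, 6 or 12 months; censoring at 18 months; half of subjects reduced to 75% dose after Cycle 3; 200 runs per setting. A four-group log-rank test at 0.05 serves only as a yardstick, since the SAP plans no test. At N = 40 and true median 6:

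| Grouping | Median observed time, Q1 | Q4 | p < 0.05 |
|---|---|---|---|
| Cumulative AUC to PFS | 1.4 | 13.3 | 100% |
| Time-average AUC | 13.4 | 2.7 | 89.5% |
| First-dose AUC | 6.5 | 6.5 | 5.5% |

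Across all settings, including clearance log-SD 0.5, the false-positive rate was 98% to 100% for cumulative AUC, 74% to 100% for time-average AUC and 4% to 12.5% for first-dose AUC. Excess over 5% in the last reflects small groups and only 200 runs. Total AUC matched cumulative AUC because dosing was assumed to stop at progression.

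**Time to response.** Among 20 responders with assumed response times of 1 to 5 cycles, unrelated to exposure, median time to response was 21 days in the lowest and 82 days in the highest quartile of cumulative AUC to response (rank correlation 0.84).

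DOR and corneal events follow the same counting argument: a later event means more doses before it.

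**The case against.** A reader might infer that the plan commits to plotting by cumulative exposure to the event. It does not. Section 16.10.2.2.2 says only exposure, first-dose quartiles sit in the same dataset, and section 16.9.2 points to Cycle 1 measures. That limits the point to an open choice. It does not remove it: the to-event quartiles are specified outcome by outcome to match the plots, the SAP gives them no other use, and nothing reconciles them with section 16.9.2.

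A reader might also infer that every such plot would show false benefit. That holds only for PFS and DOR with cumulative or total exposure. Nor does the time-average reversal need longer-treated subjects to have more delays or reductions, for which the SAP gives no evidence; the hand calculation shows it at constant dose.

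A third inference is that the dose selection would be misled. The SAP does not say these analyses support a dose choice. Section 2.3 bases the Part 2 dose on Part 1 outcomes, sections 12.1 and 16.10.2 report this work separately, and the PK/PD figures in 16.12.12 are QTc plots only. This objection stands.

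Finally, the sizes rest on assumed inputs, and pooling Part 1 doses (0.03 to 4.60 mg/kg) adds real dose variation to cumulative exposure. That is fair. In the pooled case tried, the artefact remained.

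**Conclusion.** The point holds as an unspecified metric that admits outcome-dependent groupings. Used as quartile groups, those variables would give strong false trends whose sign depends on the variable chosen. For PFS by cumulative AUC, the lowest and highest quartile medians differ by roughly 8 to 18 months under the null (8.6 − 0.6 = 8.0; 20.3 − 2.3 = 18.0) for true medians of 3 to 12 months.

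The exact sizes depend on the assumed PFS distribution, clearance and weight variability, and dosing to progression. The direction for PFS follows from counting doses up to the event. DOR and corneal toxicity were reasoned from the same mechanism and not given a size here. It is worth correcting before the analysis is run, but it concerns exploratory work only and leaves ORR untouched.

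**What to change.** In section 16.10.2.2, state that the Kaplan-Meier plots and the logistic and ordered logistic models use exposure fixed at the first dose: first-dose AUC, Cycle 1 end-of-infusion Cmax, first-cycle amount or initial dose. All are already derived with quartiles and quintiles and agree with section 16.9.2. Initial dose separates subjects only if Part 1 cohorts are included, since Part 2 starts at a single level.

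Use Ctau only with a landmark at Cycle 2 Day 1, counting time from there among subjects still event-free, because it is observed before the Cycle 2 dose and is undefined for earlier events. Use cumulative, time-average or total exposure only as a time-varying covariate or up to a stated landmark, not as quartile groups to the event.

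The cost is a few sentences and fewer plots; a time-varying Cox model, if wanted, is modest extra work. The drawback is that first-dose exposure does not reflect later dose changes, which should be said when the results are presented.
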